## **14 Statistical Methods**

No formal hypothesis testing is planned; parameter estimates will be defined using descriptive and inferential statistics.

### **14.1 General Considerations**

Inferential statistical tests will be identified as being either one- or two-sided, and the construct of the confidence limits will be defined (e.g. 90% or 95%). Exact confidence intervals will be used for all presentations.

### **14.2 Endpoint Analyses and Hypothesis Testing**

The objective of this registry is to provide contemporaneous estimates ascribed to the event rates (rate of new white lesions on DW-MRI) under commercial use conditions. No formal statistical hypotheses regarding safety or efficacy will be made. Additional summaries and tabulations may be presented by demographic and disease-related parameters.

## **15 Data Collection**

### **15.1 Required Data**

All required data for this evaluation will be collected on standardized Case Report Forms (CRFs). For the duration of the evaluation, the Physician will maintain complete and accurate documentation, including but not limited to, medical records, evaluation progress notes, laboratory reports, CRFs, device accountability logs, correspondence with the reviewing IRB/EC, sponsor and Monitor, adverse event reports, and information regarding patient discontinuation or completion of the evaluation.

The physician/institution will permit direct access to source data and documents in order for evaluation-related monitoring, audits, IRB/EC reviews, event adjudication and regulatory inspections to be performed. The physician should obtain, as part of the Data Release Consent process, permission for authorized sponsor employees, monitors or regulatory authorities to review, in confidence, and records that identify patients in this trial.

### **15.2 Source Documentation**

Regulations require that the Physician maintain information in the patient's medical records, which corroborate data collected for the evaluation. In order to comply with these regulatory requirements, at minimum, the following is a list of information that should be maintained:

- Medical history / general physical condition of the patient before involvement in the evaluation of a sufficient nature to verify the protocol eligibility criteria.
- Dated and signed notes on the date of entry into the evaluation documenting the following:

- The general health of the patient,
- Dated and signed notes from each patient visit to support all data recorded on the CRFs.
- Adverse events reported and their continuation or resolution at EACH visit, including supporting documents such as discharge summaries, catheterization lab reports, ECGs, lab results, CT/MRI reports.
- Notes regarding protocol-required and prescription medications taken during the evaluation (including start and stop dates if known).
- Patient's general health and medical condition upon completion of or withdrawal from the evaluation.

### **15.3 Case Report Forms**

Data will be accurately recorded on the Case Report Forms (CRFs) in an electronic data capture system by site personnel that have been trained on the protocol and CRF completion.

### **15.4 Record Retention**

All clinical sites will maintain all records pertaining to this evaluation for a minimum of two years (or as long as required by specific institutional guidelines) after the evaluation is discontinued. The sponsor will notify the clinical sites of the discontinuation or planned end of evaluation as well as where applicable, the Physician and/or Silk Road Medical will inform the IRB or EC/Competent Authorities

### **15.5 Confidentiality**

All data and information collected during this evaluation will be considered confidential by the Sponsor. All data used in the analysis and summary of this evaluation will be anonymous, and without reference to specific patient names. Access to patient files will be limited to authorized personnel of the Sponsor, the Physician, Clinical site research staff and authorized Regulatory Authorities. Authorized regulatory personnel have the right to inspect and copy all records pertinent to this evaluation.

## **16 Sponsor Responsibilities**

As the Sponsor, Silk Road Medical, has the overall responsibility for the conduct of the evaluation including assurance that the evaluation satisfies the regulatory requirements of the appropriate regulatory agencies.

### **16.1 Training of Physicians and Site Personnel**

Physicians and site personnel will be trained on the following aspects of the evaluation:

- Protocol
- Case Report Forms
- Reporting Responsibilities
- Device Instructions for Use
- Confidentiality

## **17 Monitoring**

The Sponsor or designee may regularly monitor the evaluation throughout its duration. Monitors will visit each site to review clinical data for accuracy and completeness and to ensure compliance with the protocol. The Monitor may inspect all documents and required records that are maintained by the Physician, including medical records (office, clinic or hospital) for the patients in this evaluation. The Physician will facilitate access to these records by authorized representatives of the Sponsor, and appropriate regulatory agencies.

A termination (close-out) monitoring visit will be conducted at the completion of the evaluation to ensure that all clinical trial materials and patient data are properly documented and stored until SRM (Sponsor) informs the Physician that data collection has been completed. The Sponsor will notify each site during the closeout visit of the current data storage requirements.

## **18 Site Responsibilities**

### **18.1 Site Personnel Responsibilities**

#### **18.1.1 Principal Physician**

- Ensures that the appropriate IRB or EC approvals are obtained as required,
- is responsible for the overall conduct of the evaluation at the site,
- is trained in the use of the devices,
- is trained on the evaluation protocol, forms, and procedures.

### **18.2 Physician Responsibilities**

The Physician is responsible for ensuring that this evaluation is conducted according to this Clinical Protocol, and all conditions of IRB/EC approval and applicable regulations. The Physician is responsible for ensuring that Data Release Consent is obtained, if required. The data release form may be translated into the applicable language.

Patients must be informed that their medical records may be subject to review by SRM (Sponsor), its authorized designee, or local regulatory representatives. Patients will be informed that they are free to refuse to participate in this evaluation without loss of benefits to which they are otherwise entitled, and that if they choose to participate, they may withdraw at any time without prejudice to future care.

#### **18.2.1 Physician Records**

The Physician will maintain complete, accurate and current evaluation records. Records shall be maintained during the evaluation and for two years (or as long as required by specific institutional guidelines) after the date on which the evaluation is terminated or completed, or the date the records are no longer required.

#### **18.2.2 Patient Records**

Patient records include copies of all completed Case Report Forms and supporting documents (laboratory reports, reports of diagnostic tests, medical records, etc.).

At any time, patients are entitled to ask the Physician for access to all the information collected in this study relating to him or her. If any of the information is inaccurate, the subject is entitled to request to the physician that the appropriate changes or corrections are made.

#### **18.2.3 IRB/EC Information**

The physician is responsible for maintaining any information pertaining to the IRB/EC review and approval as required by local law.

#### **18.2.4 Other**

The physician is responsible for any other records that may be required by applicable laws.

### **19 Core and Central Laboratories**

#### **19.1 DW-MRI Core Laboratory**

All DW-MRI evaluations will be sent to the DW-MRI core laboratory for review. The evaluation will be reviewed using a standard method per the core laboratory guidelines and these data will be used for final analysis.

### **20 Protocol Deviations**

A protocol deviation is defined as an event where the physician or site personnel deviate from the protocol or procedures.

In the event that a physician does not comply with the Physician agreement, and/or the protocol, the physician will be notified of their non-compliance, and the circumstances will be reviewed by the sponsor.

### **21 Device Accountability**

Product used in this evaluation are FDA approved/cleared and have CE marking. The devices are commercially available and device accountability is not required.

### **22 Ethics**

This evaluation is a non-interventional post market evaluation, which means that IRB/EC approval depends on local law / hospital requirements. If not required, written documentation from the physician should be maintained with the records

#### **22.1 Protocol Amendments**

Approved protocol amendments will be provided to the Physicians by the sponsor prior to implementing the amendment. The Physician will be responsible for notifying or obtaining approval from the reviewing IRB/EC of the protocol amendment, if required by local law/hospital. The IRB/EC acknowledgement/ approval of the protocol amendment must be documented in writing prior to implementation of the protocol amendment. Copies of this documentation must also be provided to the Sponsor.

## **22.2 Data Release Consent**

If required, by local law / hospital the physician should obtain written Data Release Consent prior to releasing personal information of the patient. An IRB/EC approved Data Release Consent may be required according to local law/hospital requirements.

### **22.2.1 Data Release Consenting Procedures**

During the Data Release Consent discussion, the physician or his/her designee must fully inform the subject of the evaluation in a non-technical wording understandable for the patient. The patient must have ample time and opportunity to inquire about details of the evaluation, and to decide whether or not to participate. All questions about the evaluation should be answered to the satisfaction of the patient.

After all persons have signed and dated the Data Release Consent form the physician must provide the patient with a copy of the signed and dated Data Release Consent form.

## **23 Use of Information and Publication**

All information and data generated in association with this evaluation will be held in strict confidence according to local regulation and remains the sole property of Silk Road Medical. The Physician agrees to use this information for the sole purpose of completing this evaluation and for no other purpose without written consent from the Sponsor.

At the conclusion of this evaluation, a multi-center abstract reporting the primary results may be prepared and presented in an appropriate scientific forum. A multi-center peer-reviewed manuscript may also be prepared for publication in a reputable scientific journal. The publication of the principal results from any single center experience within the evaluation will be coordinated with the Sponsor. The site shall have the right to publish their individual results but only after publication of the multi-center publication is complete, provided, however, that at least thirty (30) days prior to any submission of a publication or presentation, the site provides Silk Road Medical with a copy of the publication or presentation for Silk Road Medical's review and approval. Silk Road Medical reserves the right to delay approval either to prevent bias in ongoing clinical trials or to prevent adverse impact on the completion of the planned evaluation.

## **24 Termination**

The Sponsor will monitor the progress of the evaluation. If warranted, the evaluation may be suspended or discontinued early if there is inadequate patient enrollment.

## Appendix 1. Schedule of Events

PROCEDURE/TEST	Pre-Procedure (within # of days)					Procedure	Post-Procedure			Follow-up Visits 30-days (-7/+15 days)
	180 days	60 days	30 days	7 days	≤72 hrs		Within 24 hrs	Prior to Discharge	Within 12 – 60 hours post procedure	
Informed Consent		X								
Neurological Examinations										
NIH Stroke Scale Modified Rankin Scale				X			X			X
Imaging										
Bilateral Duplex Ultrasound (% of stenosis)		X								X
CTA 	X									
DW-MRI					X				X	X
Other Assessments										
Medical History			X							
Medications		X				X	X	X		X
Adverse events						X	X	X		X

 Must be performed by a Neurologist, NIHSS-certified personnel or other designee. Every attempt should be made to have the same person conduct the exam at each visit. The primary operator may not conduct the neurological exam on the treated patient.

 The suitability of access site and distance from the clavicle to the bifurcation (as part of standard of care) may be measured by computerized axial tomography (CT) angiography in accordance with the FDA approved labeling.

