### 7.2 Secondary Endpoints

The following secondary endpoints will be assessed 0 to 30 days:

- All Stroke
- Neurological Death
- Volume of DW-MRI lesions
- Location of DW-MRI Lesions
- Stroke/Neurological Death in patients eligible for ROADSTER 2
- Stroke/Neurological Death in patients ineligible for ROADSTER 2
- Rate of contralateral new white lesions by DW-MRI

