## 9.3 Patient Discontinuation

If possible, every patient should remain in the study until completion of the required follow-up period; however, the patient's participation in the study may be discontinued at any time during the study. If this occurs, the reason for discontinuation should be documented in the source documentation, and Study Exit form must be completed. Factors leading to patient discontinuation may include, but are not limited to the following:

- **Patient Withdrawal:** Patient participation is voluntarily and the patient may discontinue participation (refuse all subsequent testing and follow-up) or withdraw their consent from the study at any time without affecting their future medical treatment or benefits.
- **Physician Termination:** The physician may terminate the patient's participation without regard to the patient's consent if the Physician believes it is medically necessary.
- **Lost to Follow-up:** A patient will be considered lost to follow-up only after three unsuccessful, documented attempts to contact the patient have been made.

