**Table 1. DW-MRI visit windows**

Visit Window	Imaging Timing
Pre-procedure	≤ 72 hours prior to procedure
Post-procedure	Within 12 – 60 hours post procedure
30 days Post-procedure	30 days(-7/+15 days) post procedure

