**Table 6. 30-day Testing and Evaluations**

Test / Evaluation	30-days (-7/+15 days)
Neurological Examination	
NIH Stroke Scale	✓
Modified Rankin Scale	
Imaging	
Duplex Ultrasound (Bilateral)	✓
DW-MRI	✓

Every attempt should be made to have the same person conduct the exam at each visit.

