### 12.1 Clinical Follow-up Visits

Patients will be contacted for clinical follow-up office visit between 30 and 45 days post procedure.

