## **13 Adverse Events**

Adverse event (AE) data will be collected throughout the study and will be recorded on the Adverse Event CRF. For the purposes of this evaluation, adverse events include any stroke or neurological death.

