### **Minor Stroke**

NIH  $\leq 4$

Rankin  $\leq 2$

Note: If NIH  $\geq 4$  at enrollment, any change  $\leq 4$  is considered a minor stroke

**IMPORTANT:** The determination of stroke and stroke severity is based upon clinical presentation only. Imaging will not be used to confirm a diagnosis of stroke.

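### Section 12.1 puts the follow-up visit at days 30 to 45, but Table 6 and Appendix 1 allow it from day 23, so the last scheduled stroke and neurological death check can fall before the 0 to 30 day endpoints close

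*Protocol*

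**What the plan says.** Section 12.1 of the protocol says that patients will be contacted for a "clinical follow-up office visit between 30 and 45 days post procedure". It then refers to Appendix 1 for the evaluations at each time point.

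Appendix 1 has one follow-up column, headed "Follow-up Visits 30-days (-7/+15 days". Table 6 in Section 11.1 heads the same visit "30-days (-7/+15 days". The DW-MRI window table in Section 10.2 uses the same limits for the late scan: "30 days(-7/+15 days) post procedure".

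For the endpoints, Section 7.2 states: "The following secondary endpoints will be assessed 0 to 30 days". Four of the seven listed are clinical: all stroke, neurological death, and stroke or neurological death in patients eligible and in patients ineligible for ROADSTER 2. Section 13 says that "adverse events include any stroke or neurological death" and that they are collected throughout the study. In Appendix 1 the last adverse event mark and the last NIHSS mark both stand in the follow-up column. Section 12.2 leaves any further visit to clinical need.

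**The concern.** The two windows share an upper limit, but their lower limits differ by a week, and the protocol does not say which governs. A site working from Section 12.1 will ask about stroke and neurological death once the 30-day window has closed. A site working from Table 6 or Appendix 1 can ask on day 23, schedule nothing further, and still comply with the table it used.

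At stake is how completely four descriptive secondary endpoints are ascertained. Each counts events over a fixed interval. A patient who is event-free at an early visit can enter the 30-day count as event-free although the end of the interval was never asked about. Any resulting error goes one way: an event can be missed, so the rate can only be too low. Completeness could also differ between sites according to which part of the protocol they follow.

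**Working it through.** The protocol states no figure to reproduce here. The check is day arithmetic on its windows.

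**Inputs**
- Section 12.1: office visit on days 30 to 45.
- Table 6 and Appendix 1: 30 days, -7/+15.
- Section 7.2: endpoint interval, days 0 to 30.
- Appendix 1 and Section 12.2: one follow-up column, with no later scheduled contact.

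**Window in the tables.** Lower limit 30 - 7 = day 23. Upper limit 30 + 15 = day 45. Against Section 12.1, the upper limits agree (45 and 45) and the lower limits differ by 30 - 23 = 7 days.

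**Endpoint days left without a scheduled check.** For a visit on day v, this is max(0, 30 - v), and its share of the interval is max(0, 30 - v)/30.

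| Visit day | Days without a scheduled check | Share of 30 days |
|---|---|---|
| 23 | 7 | 23.3% |
| 24 | 6 | 20.0% |
| 25 | 5 | 16.7% |
| 26 | 4 | 13.3% |
| 27 | 3 | 10.0% |
| 28 | 2 | 6.7% |
| 29 | 1 | 3.3% |
| 30 to 45 | 0 | 0% |

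**Could these be two separate contacts?** Section 12.1 names an office visit and points to Appendix 1 for its content. Appendix 1 has a single follow-up column, with the -7/+15 heading. The text describes one visit with two windows.

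**Does anything else scheduled cover the gap?**
- The late DW-MRI has the same -7/+15 window, so it can also fall on day 23. Appendix 4 adds: "Imaging will not be used to confirm a diagnosis of stroke". The scan therefore cannot stand in for the clinical check.
- Section 13 collects adverse events throughout the study, which allows an event to be recorded when it comes to the site's notice. It sets no contact on or after day 30.
- Section 9.3 asks that, if possible, "every patient should remain in the study until completion of the required follow-up period", but does not give that period in days.

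**After the change.** With a clinical check at 30 days (-0/+15), the earliest last check is day 30 and the uncovered time falls from at most 7 days to 30 - 30 = 0.

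**The case against.** The strongest reply is that the texts can be followed together. A visit on days 30 to 45 satisfies Section 12.1, Table 6 and Appendix 1 at once and leaves no gap. Section 12.1 can be read as fixing the timing and Appendix 1 as listing only the content. This stands in part: the gap is permitted by the tables and is not forced by the protocol as a whole. But Appendix 1 and Table 6 carry their own explicit window, and nothing ranks them below Section 12.1, so a site that relies on either has no reason to think day 23 too early.

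A second reply is that events on days 24 to 30 remain collectable. This also stands. A reader might infer that a patient leaves the study at an early visit and that later events are lost. The documents do not say so: Section 9.3 does not define the required follow-up period, and Section 13 keeps adverse event collection open throughout the study. Such events are unscheduled, which is different from uncollected. What remains is that nobody is required to ask, and a minor stroke is the kind of event that may not be volunteered.

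A reader might also be tempted to put a number on the missed events by applying the 2.3% and 4.4% stroke/death rates in the Introduction to the uncovered days. The documents do not support that. Those rates belong to CEA and filter-protected CAS in another trial. They count stroke and death where the present endpoints use neurological death, and the Introduction gives no time window for them. The calculation would further need every patient to be seen on day 23, an even spread of events over 30 days, and no unscheduled reporting. Nor does the change that one event makes to a rate in 50 to 75 patients measure the effect of the window; it shows only that the sample is small.

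**Conclusion.** The point holds as an internal inconsistency with a limited consequence. Section 12.1 and the two tables disagree by 7 days on the earliest follow-up visit. A patient seen on days 23 to 29 has no scheduled stroke or neurological death check for the last 1 to 7 days of the endpoint interval (3.3% to 23.3% of it).

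This rests on reading Section 12.1 and Appendix 1 as the same visit, which their cross-reference supports, and on there being no other scheduled contact, which Appendix 1 shows. The protocol does not say how many patients will be seen early. If all are seen on day 30 or later, nothing is lost.

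The likely effect is a small downward bias in descriptive secondary rates. The primary DW-MRI endpoint is untouched, because its timing follows the imaging window, and Section 14 plans no hypothesis test. An analysis plan could not repair the gap afterwards, since it cannot supply an answer that was never sought. That makes the correction worth having despite its modest size.

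**What to change.** Separate the clinical check from the imaging window.

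- Keep -7/+15 days for the DW-MRI and the duplex ultrasound.
- In Table 6 and Appendix 1, set the clinical check (NIHSS and adverse events) at 30 days (-0/+15), which is the days 30 to 45 of Section 12.1. Table 6 has no adverse event row and needs one.
- If the visit is held on days 23 to 29 so that it coincides with imaging, require a telephone check for stroke and neurological death on or after day 30, with an examination if a deficit is reported. Section 12.1 then needs a sentence allowing this call.

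The cost is a minor protocol amendment, with IRB/EC notification or approval where local rules require it (Section 22.1), and one short call for each patient seen early. The downside is that a call is less sensitive than an NIHSS examination for a minor stroke between the early visit and day 30. Holding the clinical visit on day 30 or later avoids this, but may mean a second trip for a patient whose imaging was done early.

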## Appendix 2. Case Report Forms

Case Report Forms are on file separately at Silk Road Medical

Document #	Title
SRM-2018-08-CRF01	Pt Registration
SRM-2018-08-CRF02	Medical History
SRM-2018-08-CRF03	Procedure
SRM-2018-08-CRF04	Devices
SRM-2018-08-CRF05	Follow-up
SRM-2018-08-CRF06	Neuro Exam
SRM-2018-08-CRF08	Protocol Deviation
SRM-2018-08-CRF09	Adverse Events
SRM-2018-08-CRF07	Study Exit
SRM-2018-08-CRF010	DW-MRI

